8.1.1 Severity of Event

The following scale will be used to grade the severity of adverse events:

- 1) Asymptomatic or mild symptoms; no intervention needed (non-serious);
- 2) Moderate: minimal, local, or non-invasive intervention indicated; limiting on ADL (non-serious);
- 3) Severe or medically significant but not immediately life threatening; hospitalization or prolonged hospitalization needed; disabling; limited self-care ADL (serious);
- 4) Life-threatening; urgent intervention required (serious);
- 5) Death related to AE (serious).

8.1.2 Non-serious Adverse Event Reporting

Non-serious AEs will be reported annually to the IRB.

8.1.3 Serious Adverse Event Reporting

All serious AEs will be reported within 48 hours, consistent with KPWHRI IRB policy and NIH guidelines. All participants learned to be deceased, regardless of the cause of death or relatedness to the program, will be reported to the IRB. The IRB will work with the PI to ensure additional agencies (e.g., NIH, etc.) are notified as required. All SAEs will be followed until satisfactory resolution or until the PI deems the event to be chronic or the patient to be stable.

8.1.4 Expected Adverse Reactions

Expected adverse events include:

- Upset due to participation in research assessments. Such reactions are expected to be mild and transient.
- Nicotine withdrawal. Participants who chose to quit smoking may experience nicotine withdrawal symptoms such as irritability, cravings to smoke, difficulty concentrating, headache, constipation, and trouble sleeping.

- NRT side-effects. Participants who chose to use the optional OTC NRT patches may experience side-effects such as rash/skin irritation at patch site, headache, nausea, and indigestion. These adverse events are expected, transient, and generally mild to moderate intensity. While NRT use is considered safer than smoking, female participants will be advised to use birth control while using NRT.

8.2 Time Period and Frequency for Event Assessment and Follow-Up

Reportable events will be recorded in the data collection system throughout the study. Events will be followed for outcome information until resolution or stabilization.

The PI will record all reportable events with start dates occurring any time after informed consent is obtained until 7 (for non-serious AEs) or 30 days (for SAEs) after the last day of study participation.

8.3 Characteristics of an Adverse Event

8.3.1 Relationship to Study Intervention

The Study PI will determine if AE's are deemed possibly related to the individual's study involvement. The following guidelines will be used.

- Associated – The event is temporally related to the study participation and no other etiology explains the event.
- Not Associated – The event is temporally independent of study participation and/or the event appears to be explained by another etiology

8.3.2 Expectedness of SAEs

The Study PI will be responsible for determining whether an SAE is expected or unexpected. An adverse event will be considered unexpected if the nature, severity, or frequency of the event is not consistent with the risk information previously described for the intervention.

8.4 Unanticipated Problem

8.4.1 Definition

The Office for Human Research Protections (OHRP) considers unanticipated problems (UP) involving risks to subjects or others to include, in general, any incident, experience, or outcome that meets all of the following criteria:

- Unexpected in terms of nature, severity, or frequency given (a) the research procedures that are described in the protocol-related documents, such as the IRB-approved research protocol and informed consent document; and (b) the characteristics of the subject population being studied;
- Related or possibly related to participation in the research (“possibly related” means there is a reasonable possibility that the incident, experience, or outcome may have been caused by the procedures involved in the research); and

- Suggests that the research places subjects or others at a greater risk of harm (including physical, psychological, economic, or social harm) than was previously known or recognized.

8.4.2 Unanticipated Problems Reporting to IRB and NCI

Incidents or events that meet the OHRP criteria for unanticipated problems will be reported to the IRB within 48 hours of when the team is made aware of the event.

Unanticipated problem reports will include:

- Appropriate identifying information for the research protocol, such as the title, investigator's name, and the IRB project number;
- A detailed description of the adverse event, incident, experience, or outcome;
- An explanation of the basis for determining that the adverse event, incident, experience, or outcome represents an unanticipated problem;
- A description of any changes to the protocol or other corrective actions that have been taken or are proposed in response to the unanticipated problem

The IRB will determine if other immediate action is required (e.g., suspension of recruitment, protocol closure, etc.). Temporary or permanent suspension of an NIH-funded protocol will be reported to the NCI Program Official responsible for the grant.

8.5 Halting Rules

Study halting may occur as required by the IRB or NCI. The study PI may temporarily suspend enrollment pending review by these authorities if warranted based on the presence, type, or frequency of SAE's or other changes in the study protocol which may place participants at greater than anticipated risk.

9 CLINICAL SITE MONITORING

Clinical site monitoring will not be done for this study; however, the NCI reserves the right to conduct independent audits or clinical monitoring as necessary.

10 STATISTICAL CONSIDERATIONS

10.1 Study Hypotheses

We hypothesize that by engaging in the experiments, ambivalent smokers in the intervention arm will have successive mastery experiences which will build their confidence and positive outcome expectations (i.e., belief that *I can control my smoking* or *I can quit when I am ready*) and, in turn, will better motivate them to change their smoking behavior, including making a successful quit attempt and, possibly, quitting smoking. We also expect that experimental participants will be more likely to use the provided nicotine replacement patches and tobacco quitline referral than are control participants.

10.2 Sample Size Considerations

The primary analytic goals of this pilot study are to assess feasibility and to estimate the magnitude of intervention effects on study outcomes. The target sample size ($n = 60$) for this pilot is based on recommended guidelines for estimating effect sizes in behavioral treatment development research²² and not on our anticipated intervention effect size. By design, the pilot trial is not powered to evaluate efficacy or to test for statistically significant differences between intervention groups.

10.3 Final Statistical Analysis Plan

All summaries and analyses will be limited to randomized individuals who installed the app using a modified intent-to-treat approach, whereby participants are labeled by their randomization group regardless of app usage. However, when assessing self-reported satisfaction with specific app features, analyses will be restricted to participants who both self-report use of the feature and whose automated data confirm this use. This is done to eliminate ratings from people who either did not use each feature or recall its use, both of which could invalidate users' ratings.

First, descriptive statistics will be used to characterize the baseline sample. Summaries across arms for outcomes of interest 1- and/or 3-months post-baseline will be conducted in addition to counts of Experiments completed in the experimental arm.

Similar statistical methodology will be used to conduct inference for all outcomes. Regression models will be fit using generalized estimating equations with robust standard errors and an exchangeable working correlation. When applicable for a given outcome, the regression model will be fit to outcomes collected at both time points simultaneously, even if reported separately. For each binary outcome of interest—such as 7-day PPA and having a successful 24-hour smoking quit attempt—we will initially attempt to estimate relative risks (RR) of the outcome in the experimental app relative to the control app using a Poisson regression model. When outcomes are too rare to obtain estimates of relative risks, we will fit linear regression models to binary outcomes and estimate risk differences (RD) of the outcome instead. Linear

regression models will be fit to continuous outcome data—including number of program log-ins, Likert scales for self-efficacy and satisfaction and average number of cigarettes smoked per day—to estimate mean differences in the outcome across app versions. All point estimates will be accompanied by 95% confidence intervals and *P*-values from two-sided Wald tests.

All app comparisons will adjust for the assigned app, number of cigarettes smoked at baseline, and when applicable, the time of survey collection and interaction between follow-up time and assigned app. The latter interaction allows for results to be presented separately at one and 3-months post-baseline. If the outcome measure is collected at baseline and not identical across all participants at baseline, we will additionally adjust for the outcome measure at baseline. With this adjustment, the estimated average difference across study arms may also be interpreted as the average difference in change from baseline across arms. Depending on differences identified between arms at baseline that were not avoided despite randomization by chance, additional potential confounders may be adjusted for.

Outcomes collected via follow-up surveys are subject to missingness; however, per convention, missing data for smoking cessation outcomes will be imputed as smoking or failing to successfully quit smoking for at least 24 hours. For these outcomes, additional sensitivity analyses will be conducted using (1) complete cases only and (2) completed assessments using multiple imputation by chained equation²⁴ with 10 imputed data sets created with logistic regression imputation using Barnard-Rubin adjusted degrees of freedom²⁵. For all other outcomes, analyses will use complete cases only. Further sensitivity analyses may consider modification of the effect of intervention on the primary outcomes by gender.

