Population	
Participants will be recruited nationwide via advertisements on online platforms. The team will also reach out to individuals who’d previously requested to be placed on the waiting list for tobacco studies at KPWHRI.
 
The study will recruit smokers (18 and older) who want to quit smoking someday, but not in the next month, and who are not actively using or seeking treatment to quit; own and use a smartphone at least once a week and have (or are willing to upgrade to) a current iOS or Android operating system supported by the app; are willing to install and use the study program; are current smokers and smoke at least 10 cigarettes a day (as required for use of nicotine replacement therapy); speak/read English; and are willing to use birth control if they elect to use nicotine replacement therapy

	(females). Only one member per household will be eligible. Only those installing the app will be included in the final analytic sample.
Number of Sites	This pilot study includes 1 site (KPWHRI).
Description of Intervention	
We have designed a mHealth app which blends sound scientific theory, evidence-based treatment, and best practice treatment guidelines for nicotine dependence with intervention content that is also responsive to the needs and preferences of ambivalent smokers.
 
The experimental intervention combines the following components:
 
 • Best-practice self-help guidance for quitting based on the US PHS' Clinical Practice Guidelines for treating nicotine dependence and best practice treatment recommendations (aka, Quit Guide) • A toolkit with other experimental features. • A referral to free local state tobacco quitline services . • The ability to earn and request a free 2-week starter kit of nicotine replacement patches • A series of 9 personal experiments, each designed to build motivation or teach the skills necessary to successfully cu-back or quit smoking. 
The control intervention also includes items 1-4 above.

Study Duration	The pilot will be carried out over a ~1 year period.
Subject Participation Duration	Each participant will be enrolled for a period of ~3 months.
Estimated Time to Complete Enrollment	Enrollment will occur over an ~8-month period.

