2.2 Study Outcome Measures

As a pilot study, we do not have a single “primary outcome” of interest. Rather, we will examine a range of measures designed to inform our study objectives: assess the program’s feasibility (program engagement), acceptability (ratings of satisfaction and helpfulness), impact on cognitive mediators of change (self-efficacy, outcome expectations, and motivation) and impact on indicators of smoking behavior change (quit attempts, smoking reduction, and abstinence).

Outcomes will be used to assess whether the intervention warrants further refinement and whether a future randomized efficacy trial is warranted.

2.2.1 *Primary*

The primary outcomes of interest that will be explored are:

- Seven-day point prevalence abstinence (PPA) at 3-month follow up;
- Total program log-ins to the assigned program during the study period at 3 months post-enrollment;
- Self-reported presence of an intentional quit attempt lasting at least 24 hours since study enrollment by 3-month follow up.

2.2.2 *Secondary*

Key secondary outcomes that will be explored at the 1-month follow up only:

- Self-report of no smoking in the past 7 days.

Key secondary outcomes to be explored at both the 1 and 3-month follow up include:

- Overall satisfaction with assigned program;
- Helpfulness ratings for each personal experiment, as well as satisfaction ratings of the associated experimental program features;
- Self-report rating of motivation for quitting;
- Self-report ratings of self-efficacy for quitting smoking;

Secondary outcomes to be explored at the 3-month follow up only:

- Cumulative duration of assigned program utilization in minutes, based on automated program tracking data.

2.2.3 *Other Secondary & Exploratory Outcomes*

Given the exploratory nature of this pilot study we will also examine a range of other potential secondary outcomes to include: program duration days, number of days quit attempts were maintained, any quit attempt, NRT earned, NRT requested, NRT used, program component contact time, use of each intervention component, number of personal experiments completed, stage of change, utilization badges earned, change in smoking rate, and self-reported outcome expectations, motivation and self-efficacy for staying quit; self-efficacy for enacting related behavioral skills targeted in the experimental intervention.

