3.4 Treatment Assignment Procedures

3.4.1 Randomization Procedures

Randomization will be automated using a stratified block randomization scheme. Participants will be randomized following completion of the online baseline survey. We will stratify by cigarettes per day (>15 vs. <15) and frequency of smartphone use (daily vs. non-daily) since these factors might influence quitting smoking and program participation. Half will be randomized to each of the two study arms (control vs. experimental). Following randomization, participants will receive instructions on how to download and set up and access their assigned program on their smart phone.

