5.2 Baseline and Randomization

Consenting participants will be emailed a link to complete the online baseline survey. Following completion of the baseline survey, they will be automatically randomized and provided instructions for accessing their assigned version of the app on their smartphone. Staff will be available to assist with this, as needed. Randomization date is Day 0.

5.3 1 and 3-month Follow-up Assessments

Self-reported follow-up data will be assessed at 1 and 3-months post-enrollment using an online survey with phone follow-up.

Following completion of all study activities (3 month assessment and cotinine verification, if applicable, or a failure to complete the 3 month survey in the allowed timeframe), staff will turn off participant's access to the app from the back-end administrative dashboard.

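### Randomized people who never install the app drop out of every summary and no installation proportion is planned, so the engagement outcomes cannot show failure to install

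*Combined protocol and SAP*

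**What the plan says.** **Order of events.** Section 5.2 says that once the baseline survey is done, "they will be automatically randomized and provided instructions for accessing their assigned version of the app on their smartphone", and it sets the randomization date as Day 0. Section 3.4.1 agrees: "Following randomization, participants will receive instructions on how to download and set up and access their assigned program on their smart phone".

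**Analysis population.** Section 10.3: "All summaries and analyses will be limited to randomized individuals who installed the app using a modified intent-to-treat approach". The Population entry of the Protocol Summary repeats it: "Only those installing the app will be included in the final analytic sample". Section 3.2 also lists non-installation during the study as an exclusion. Within the retained group, section 10.3 adds that "participants are labeled by their randomization group regardless of app usage".

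**What is measured.** Section 2.2 defines two of the aims as "feasibility (program engagement), acceptability (ratings of satisfaction and helpfulness"). A primary outcome is "Total program log-ins to the assigned program during the study period at 3 months post-enrollment", and a secondary outcome is "Cumulative duration of assigned program utilization in minutes, based on automated program tracking data". Section 4.3 tracks log-ins, features used and time in the program.

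**What is not there.** Installation, as a count or a proportion, does not appear in the outcome lists of section 2.2 (including the long exploratory list), in section 4.3 or in section 10.3. The sensitivity analyses in section 10.3 (complete cases, multiple imputation) deal with missing surveys among installers. None brings in people who did not install.

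**The concern.** The restriction is openly declared and consistently worded, so this is not a contradiction. The difficulty is that the population is defined by something that happens after randomization and that is itself part of feasibility. For an app offered to smokers who do not plan to quit within a month, not installing it is the first way engagement can fail. The planned outcomes begin only after that step has been passed.

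Low use after installation is still captured, because installers stay in however little they use the app. Failure to install is not captured.

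Section 10.2 gives the analytic goals as assessing feasibility and estimating effect sizes, and section 2.1 says the pilot is to help plan a later efficacy trial. A planner who reads engagement per installer as engagement per person randomized will be too optimistic, and the plan does not supply the figure needed to correct it.

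**Working it through.** **Inputs.** From the documents: target n = 60 and equal allocation (sections 10.2 and 3.4.1). The target rests on pilot-study guidance and not on a power formula, so there is no calculation to reproduce. The documents give no non-installation proportion q, no mean or SD of log-ins and no cessation rates. Every such value below is an assumption.

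**1. Mean engagement.** A non-installer has 0 log-ins and 0 minutes. These are known values, not missing ones. So

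mean over all randomized = (1 − q) × mean among installers,

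and the installer mean exceeds the all-randomized mean by 1/(1 − q). With 60 randomized and an assumed installer mean of 10 log-ins:

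| q | Installed / randomized | Wilson 95% CI for installation | 1/(1 − q) | Planned mean | Mean over all randomized |
|---|---|---|---|---|---|
| 0% | 60/60 | 94.0% to 100% | 1.00 | 10 | 10.0 |
| 5% | 57/60 | 86.3% to 98.3% | 1.05 | 10 | 9.5 |
| 10% | 54/60 | 79.9% to 95.3% | 1.11 | 10 | 9.0 |
| 20% | 48/60 | 68.2% to 88.2% | 1.25 | 10 | 8.0 |
| 30% | 42/60 | 57.5% to 80.1% | 1.43 | 10 | 7.0 |

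The planned summary is 10 in every row. At q = 2% the factor is 1/0.98 = 1.02. The confidence intervals show how precisely a study of this size would estimate installation.

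**2. Spread.** Adding zeros also widens the distribution. With s = 1 − q and CV = SD/mean among installers,

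CV_all² = (CV² + 1)/s − 1.

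With CV = 1 assumed, CV_all is 1.05, 1.11, 1.22 and 1.36 at q = 5%, 10%, 20% and 30%. The sample needed to detect a given relative difference is proportional to CV². Under equal uptake, the ratio CV_all²/CV² is therefore 1.11, 1.22, 1.50 and 1.86. At q = 20% it is 1.69 if CV = 0.75 and 1.36 if CV = 1.5. Check with mean 15, SD 15, s = 0.8: the all-randomized mean is 12.0 and the SD 14.70, and 14.70/12.0 = 1.225. These ratios matter only if a later trial is sized on log-ins and analysed as randomized.

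**3. Cessation under equal uptake.** Assume 24 of 30 install in each arm, with non-installers counted as smoking:

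- Installers: 6/24 against 3/24, RR = 2.0, RD = 25.0 − 12.5 = 12.5 points.
- All randomized: 6/30 against 3/30, RR = 2.0, RD = 20.0 − 10.0 = 10.0 points.

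The unadjusted relative risk does not move. Absolute rates and differences shrink.

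**4. Unequal uptake, for illustration only.** If 27/30 install in one arm and 21/30 in the other, with an installer mean of 10 in both, the planned difference is 0. The all-randomized difference is 9.0 − 7.0 = 2.0 log-ins. Nothing in the documents suggests that this happened.

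**5. Meaning of n = 60.** Section 10.2 does not say whether 60 counts people randomized or installers. If installers, the number to randomize is 60/(1 − q), rounded up: 64, 67, 75 or 86 at q = 5%, 10%, 20% or 30%.

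**The case against.** **The plan never claims to report use per person randomized.** It names installers as its population and estimates engagement in them correctly. This stands: the planned estimate is not in error for the population it names. What is missing is the step before it, in a study whose stated goal is feasibility.

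**Non-installers are excluded by section 3.2, and section 3.5.1 lets the investigator end participation when an exclusion is newly met or recognized.** That does not settle the matter, because this exclusion can be applied only after an arm has been assigned.

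**Between-arm bias is unlikely.** Participants are blinded to arm (section 3.4.2), and non-installation comes before any contact with app content. Accepted. The point concerns the feasibility estimate, not a biased comparison.

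**The size is unknown and may be small.** Eligibility requires willingness to install (section 3.1), and staff help with access (section 5.2). Both may keep q low, but the plan would not show whether they did. The sample-size ratios rest on several assumptions and should be read only as illustration.

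**Counts may appear in a flow diagram or the Manual of Procedures.** Possibly. The section 10.3 population cannot be formed without knowing who installed. But neither document plans to report it, and section 10.3 restricts all summaries to installers.

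**Once the proportion is reported, anyone can multiply.** True for the mean, but not for the spread or for an adjusted difference with its interval.

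**Conclusion.** The concern holds. Installation follows randomization, every summary is limited to installers, and no installation proportion or all-randomized analysis is planned. The log-in and minute outcomes therefore cannot show failure to install.

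Taken as a measure per person randomized, the planned mean is too high by 1.05 to 1.43 times for assumed non-installation of 5% to 30%, and the effect is minor at 5% or less. No between-arm bias is shown, and under equal uptake the unadjusted cessation relative risk is unaffected. Confidence in the gap is high. Its size cannot be known from the documents. It should be fixed because it touches a core feasibility measure and the remedy is cheap.

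**What to change.** Amend sections 2.2 and 10.3 as follows:

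1. Report the numbers randomized and installed by arm, and give the installation proportion with its 95% confidence interval as a feasibility outcome.
2. Analyse log-ins and minutes in all randomized participants, with non-installers set to 0, using the planned linear model. Keep the installer-only analysis beside it, labelled as such. The main covariate, baseline cigarettes, is collected before randomization, so the model can be fitted.
3. As a sensitivity analysis only, repeat the abstinence and quit-attempt analyses in all randomized participants under the existing rule that treats missing outcomes as smoking or no quit attempt. State how many non-installers were imputed.

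Satisfaction and the other complete-case measures stay installer-only. Two optional clarifications: say in section 3.2 that the non-installation criterion can be applied only after randomization, and say in section 10.2 whether 60 means randomized or installers.

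**Cost.** SAP wording and a little extra analysis, with no change to conduct. Items 1 and 2 need randomization records, installation status (which section 10.3 already requires) and the tracking data in section 4.3. Section 3.5.2 keeps data from complete withdrawals only with consent, so any gaps should be stated. Item 3 may add mostly imputed smokers, since the documents do not show that non-installers were surveyed. Engagement figures will look less favourable. Section 5.4 shows that follow-up had begun before this final plan was written, so the additions should be labelled as made at that stage.

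### Section 10.3 names no small-sample correction for its linear GEE analyses; done the default way, nominal 95% intervals for log-ins and Likert outcomes cover about 93–94% at n = 60

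*Combined protocol and SAP*

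**What the plan says.** Section 10.3 sets one method of inference for all outcomes: "Regression models will be fit using generalized estimating equations with robust standard errors and an exchangeable working correlation". It continues: "All point estimates will be accompanied by 95% confidence intervals and" P-values from two-sided Wald tests. Linear models are used for continuous outcomes, "including number of program log-ins, Likert scales for self-efficacy and satisfaction and average number of cigarettes smoked per day". Every model contains arm and baseline cigarettes. Time, arm-by-time and the baseline value of the outcome are added where they apply.

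Two rules reduce the number analysed. For outcomes other than cessation: "For all other outcomes, analyses will use complete cases only". For satisfaction with specific features, "analyses will be restricted to participants who both self-report use of the feature and whose automated data confirm this use".

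The only small-sample device in 10.3 belongs to the multiple-imputation sensitivity analysis of the cessation outcomes: "logistic regression imputation using Barnard-Rubin adjusted degrees of freedom". It does not reach log-ins, Likert scales or cigarettes per day.

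Section 10.2 gives the size: "The target sample size ($n = 60$) for this pilot". It also names, as a primary analytic goal, "to estimate the magnitude of intervention effects on study outcomes".

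**The concern.** The uncorrected sandwich is biased downward in small samples because it uses fitted residuals, which are smaller than the true errors. A normal reference then ignores the uncertainty in the estimated variance. Both make the interval too short. Section 10.3 names neither a corrected variance nor a t reference, so an analyst who follows it with default settings would get both effects.

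The linear models cover total log-ins (one of the three outcomes listed as primary in section 2.2.1), ratings of motivation, self-efficacy and satisfaction, and cigarettes per day. The pilot is not powered for testing and is meant to help plan an efficacy trial (section 2.1), so the interval around each effect is a main product. A 95% label should mean close to 95%.

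**Working it through.** **Inputs from the documents.** Target n = 60 (10.2), allocated 1:1, about 30 per arm (3.4.1). Nominal level 95% (10.3). Regression parameters, counting the intercept: 3 for log-ins (intercept, arm, baseline cigarettes), 4 for a single time point with a baseline value, and 6 for two time points with time, arm-by-time and a baseline value.

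**Assumed, because the documents give no figure.** Outcome distributions, within-person correlation, missingness, and numbers of feature users.

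**The plan's own figure.** The only stated value is the nominal 95%. The sample size comes from pilot guidelines, so there is no power calculation to reproduce.

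**Step 1: approximation.** For one normal outcome per person, the uncorrected sandwich is too small by about √((n−p)/n). Coverage with z is then about 2·T(1.96·√((n−p)/n)) − 1, where T is the t distribution function on n−p degrees of freedom.

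| n | p | √((n−p)/n) | Approximate coverage |
|---|---|---|---|
| 60 | 3 | 0.975 | 93.9% |
| 60 | 4 | 0.966 | 93.7% |
| 60 | 5 | 0.957 | 93.4% |
| 60 | 6 | 0.949 | 93.2% |
| 30 | 3 | 0.949 | 92.6% |
| 20 | 3 | 0.922 | 91.2% |
| 16 | 3 | 0.901 | 89.9% |

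**Step 2: simulation at n = 60.** Models follow the 10.3 covariates. The single-time-point cells use 20,000 replicates (Monte Carlo standard error about 0.2 points), with HC2 as the analogue of Kauermann-Carroll (KC). The two-time-point GEE cells use 5,000–6,000 (about 0.35 points).

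| Outcome | Plain sandwich, z | KC, t(n−p) |
|---|---|---|
| Likert or normal, one time point, baseline adjusted | 93.3–93.4% | 94.7–94.9% |
| Two-time-point GEE, 3-month contrast | 93.6% | 94.7% |
| Same, 20% missing | 93.1% | 94.7% |
| Log-ins, negative binomial, mean 15, k 0.7–1.5, no effect | 94.1–94.2% | 95.2–95.4% |
| Log-ins, means 10 vs 20 | 92.4% | 93.6% |

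A second simulation with separate code gave these results for the plain sandwich with z:
- Likert outcomes: 94.0% with no missing data, 93.1% with 30% missing.
- Log-ins, no effect: 94.1–94.3% (93.4% from a standard GEE package, 4,000 runs).
- Log-ins, mean doubled from 10: 93.0%, 92.7%, 92.5% and 91.3% at dispersion 1, 1.5, 2 and 3.

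**Step 3: feature-user subsets.** No baseline term. The user counts are hypothetical.

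| Users per arm | Plain sandwich, z |
|---|---|
| 15 | 92.2–93.0% |
| 12 | 91.4–91.8% |
| 10 | 90.7–91.1% |
| 8 | 89.3–90.4% |
| 15 vs 8 | 90.4% |

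With KC and t, coverage in these cells is 94.0–95.3%.

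**Step 4: outcomes outside the point.** Poisson relative risks at n = 60 cover 95.5% (risk 0.4–0.6), 97.0% (0.2) and 99.2% (0.1), leaving out samples with no events in an arm. For the risk-difference fallback the correction adds only 0.2–1.7 points, and it does not repair the case of zero events in one arm. The personal experiments exist in one arm only, so their ratings have no arm contrast.

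**Step 5: cost in width.** At n = 60 with 4 parameters the ratio is 1/√(1 − 4/60) × 2.003/1.960 = 1.058, and the simulated value is also 1.058.

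**The case against.** The plan's silence excludes nothing. Robust standard errors and Wald tests are compatible with a corrected sandwich and a t reference, and no GEE software is named. This stands: the shortfall exists only if the defaults are used.

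The effect is also small. Take an assumed Likert SD of 1.0–1.2 and ignore any gain from baseline adjustment. The plain half-width is 1.96 × SD × √(2/30) × 0.955 = 0.48 to 0.58, where 0.955 is the simulated ratio of mean plain standard error to true SD. Multiplied by 1.058 this becomes 0.51 to 0.61, a change of about 0.03 of a scale point. Point estimates do not move. This stands too, and it limits the weight of the point. It does not make a 93% interval a 95% one.

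For log-ins with unequal means, coverage falls a little below 93–94%, and the correction recovers only part of the gap. What remains comes from skewness and unequal variance, which the correction does not address. This is right: the 93–94% range slightly understates the shortfall in that case.

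The lowest coverages rest on invented user counts, and section 2.2.2 leaves some doubt whether ratings of shared features will be compared between arms. They should be read as illustrations.

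Finally, other corrections work. Mancl-DeRouen with z gave 94.9–95.3% for Likert outcomes. Kauermann-Carroll is therefore a sound choice, but not the only one.

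**Conclusion.** The point holds as a minor one. Section 10.3 names no small-sample correction for its linear GEE analyses. With the plain sandwich and a normal reference, nominal 95% intervals cover about 93–94% at n = 60 for Likert-type outcomes and for log-ins with no effect. For skewed log-ins with a doubled mean they cover about 91–93%. The shortfall is usually 1 to 2 points at the full sample and would be larger in small feature-user subsets.

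These figures rest on default software behaviour and on assumed distributions, missingness and user counts. The direction does not depend on skewness, since normal outcomes show it too. Two of the three primary outcomes, abstinence and quit attempts, are unaffected when analysed as Poisson relative risks. Nothing here would change the pilot's conclusions.

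**What to change.** After the sentence in 10.3 on Wald tests, add:

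> For all linear-model GEE analyses, including feature-user subsets, robust standard errors will use the Kauermann-Carroll bias correction. Confidence intervals and P-values will use a t distribution with degrees of freedom equal to the number of participants in the model minus the number of regression parameters. Poisson relative-risk analyses will use ordinary robust standard errors.

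The risk-difference fallback is also a linear model and can take the same wording, with little gain.

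The cost is one sentence and a software option. Design, sample size and data collection stay as they are. Intervals become wider: about 5–6% at n = 60, 10% at n = 30, 13% at n = 24, 17% at n = 20 and 22–24% at n = 16. Section 5.4 describes 3-month follow-up in the past tense, so outcomes may already have been seen. If so, the change should be reported as made after the fact.
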